4.12 Inclusion Criteria

Candidates for this study must meet **ALL** of the following Inclusion criteria:

1. Subjects who are ≥ 30 and < 79 years of age; inclusive of males and females.
2. Subjects with a history of confirmed Barrett's esophagus with dysplasia (low-grade or high-grade) refractory to radiofrequency ablation 3 times.
3. Residual Barrett's length is ≥ 1 cm and ≤ 6 cm.
4. Histologic persistence of intestinal metaplasia (any non-squamous epithelial lesion) following treatment and failed eradication.
5. Following 3 failed RFA procedures with no confirmed evidence of EAC and having confirmed no endoscopic and histologic evidence of EAC at the time of therapy.
6. Subject capable of giving informed consent.
7. Subject has a reasonable expectation for prolonged survival (greater than 5 years).
8. Subject can tolerate repeated endoscopic procedures.
9. Absence of strictures that preclude the passage of the endoscope.
10. Subjects with the ability to understand the requirements of the study, who have provided written informed consent, and who are willing and able to return for the required follow-up assessments through 6 months or 9 months, as indicated.

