5.5.3 Index Procedure

Once enrolled, each patient will be randomized into either the EndoRotor® mucosal resection arm or the control ablation arm. Randomization will occur within 2 weeks of the procedure. The investigators shall follow the technique described by the manufacturer's instructions as provided in the Instructions for Use.

Endoscopic treatment of the esophagus will be performed within 6 weeks of enrollment with outpatient video documentation of the residual Barrett's changes during upper endoscopy.

EndoRotor® Arm: At this point, the EndoRotor® will be set-up and used to resect the mucosa and submucosa to remove all gross visible disease. Lesions will be "lifted" using saline solution with dye such as Indigo carmine or Methylene Blue. Indelible ink (such as SPOT) will be injected into the region of the resection to identify the site after resection. If the lesion is circumferential, the endoscopist shall resect no greater than 270 degrees of the radial circumference of the esophagus to avoid stricture formation. The resection is taken down to the muscularis propria layer to ensure all of the mucosa and submucosa is removed in the area of persistence.

The EndoRotor® is set to either High Speed (1700 RPM) or low speed (1000 RPM) based on user preference and the vacuum is set to between 250 mmHg and 350 mmHg of negative pressure. The endoscopist will start the EndoRotor® motor using the left foot pedal, and will activate the cutting by depressing and holding the

right pedal down for as long as he wants to resect tissue. The procedure is repeated until the entire gross visible lesion has been removed down to the muscularis propria without entering the muscle layer. The specimen can be sent to Pathology by removing the filter in the specimen trap. A new filter is placed in the specimen trap allowing multiple lesions to be treated and analyzed histopathologically.

Continued Ablative Therapy Arm: The investigator shall exercise standard of care for continued ablative therapies namely RFA (HALO 90/60) and/or cleared cryotherapy devices. These will constitute two control devices. The investigator will choose the system in this arm. Operation of the each system will be done according to the manufacturer's instructions for use. The type of system used will be indicated on the case report forms.

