7.3 Sample Size

Assuming a response rate for Barrett's esophagus with EndoRotor® ablative therapy of 80%, and for cryoablation of 50%, the study will have over 95% power to demonstrate non-inferiority (NI), given a NI delta of 10%, of EndoRotor® to cryoablation and will have 91.6% power to demonstrate superiority of EndoRotor® over continued ablative therapy using a sample size of 110 evaluable subjects, 55 in each treatment group.

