7.4 Statistical Analysis

The Primary effectiveness endpoint will be compared across treatment arms using a logistic regression, where the predictor variable is treatment arm with EndoRotor® coded 1 vs 0 for cryotherapy or ablative therapy (i.e., control). Covariates included in the model will be: subject's age, dysplasia (low-grade or high-grade), length of Barrett's lesion in cm, and duration of disease (months). The lower boundary of the predicted proportion

difference will be used to compare the two arms for the non-inferiority test and for the subsequent superiority test. In the event that missing data are present in the ITT analysis population, then multiple imputation will be performed with SAS procedures MIIMPUTE and MIANALYZE, as described in section 7.5.

The secondary endpoint, percentage reduction, will be compared using a Wilcoxon rank-sum test. In the event of missing data, The ITT analysis will be performed with data imputed by multiple imputation.

In the event of missing data, sensitivity analyses will be performed for the ITT analysis population using best case and worst case analyses as described below. Discrepant findings will be followed by tipping point analyses.

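### Sections 4.7 and 7.3 state non-inferiority power against cryoablation, but the arm tested is a pooled, investigator-chosen mix of RFA and/or cryotherapy

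*Combined protocol and SAP*

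**What the plan says.** Section 4.12 admits subjects whose dysplastic Barrett's esophagus is "refractory to radiofrequency ablation 3 times". Section 5.5.3 describes the control as standard-of-care ablation, "namely RFA (HALO 90/60) and/or cleared cryotherapy devices", and adds "These will constitute two control devices. The investigator will choose the system in this arm". Randomization is to an arm and not to a named control system: "each patient will be randomized into either the EndoRotor® mucosal resection arm or the control ablation arm". The system is captured afterwards: "The type of system used will be indicated on the case report forms". Section 5.2 randomizes 1:1 separately within each site and mentions no stratification by intended control system.

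The primary model in Section 7.4 pools the controls, with "treatment arm with EndoRotor® coded 1 vs 0 for cryotherapy or ablative therapy (i.e., control" as the coding. Its covariates are age, dysplasia grade, lesion length and disease duration. There is no term for control system and no analysis by system. The hypotheses in Section 7.6 compare EndoRotor with the control arm as a whole.

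The sample-size text is worded differently. Sections 4.7 and 7.3 assume 80% response for EndoRotor and 50% for cryoablation, and give no RFA rate. In Section 7.3 the comparator changes within one sentence. Non-inferiority power is "of EndoRotor® to cryoablation and will have 91.6% power to demonstrate superiority of EndoRotor® over continued ablative therapy". Section 4.7 makes the same switch.

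**The concern.** The non-inferiority comparator named in 4.7 and 7.3 is not the arm tested in 7.4 and 7.6. The difference matters here because one of the two control systems is the therapy that every subject has already failed three times. If repeat RFA does worse than cryotherapy in these subjects, each control given RFA lowers the pooled control rate. EndoRotor could then clear the 10-point margin against the pool while being a full margin worse than cryotherapy. A report that carried the wording of 7.3 forward would claim something the test does not show.

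The data may also be unable to settle the matter later. The plan records the system used for controls, but no rule requires the investigator to state before randomization which system a subject would receive if allocated to control. At a site that uses both systems, EndoRotor subjects therefore have no identified counterparts among the cryotherapy controls, and a comparison restricted to those controls would not be randomized.

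**Working it through.** **Inputs from the plan.** 55 evaluable subjects per arm; EndoRotor 80%; cryoablation 50%; margin 10 points (Section 7.3). Non-inferiority is judged by the lower limit of a two-sided 95% CI (Section 7.8). The checks below use unadjusted normal approximations, not the covariate-adjusted model.

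**Step 1: reproduce the stated power.**

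- Superiority, pooled-variance test, 80% vs 50%: null SE = √(0.65 × 0.35 × 2/55) = 0.0910; alternative SE = √((0.16 + 0.25)/55) = 0.0863. Power = Φ((0.30 − 1.96 × 0.0910)/0.0863) = Φ(1.41) = 92.1%. The plan states 91.6% in 7.3 and 90% in 4.7.
- Non-inferiority: Φ((0.80 − 0.50 + 0.10)/0.0863 − 1.96) = Φ(2.67) = 99.6%. The plan states over 95%.

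The arithmetic is sound. The issue is which comparator the 50% describes.

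**Step 2: how often the pooled test would wrongly support non-inferiority to cryotherapy.** Set cryotherapy at 50% (the plan's figure) and EndoRotor at 40%, exactly one margin worse. With RFA share w and RFA response r (both assumed; the documents give neither):

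- pooled control rate pC = 0.50 − w × (0.50 − r)
- SE = √((0.40 × 0.60 + pC(1 − pC))/55)
- probability of declaring non-inferiority = Φ((0.40 − pC + 0.10)/SE − 1.96)

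Worked case, w = 0.5 and r = 30%: pC = 0.40; SE = √(0.48/55) = 0.0934; Φ(0.10/0.0934 − 1.96) = Φ(−0.89) = 18.7%.

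| Assumed RFA response | 25% RFA | 50% RFA | 75% RFA |
|---|---|---|---|
| 50% | 2.5% | 2.5% | 2.5% |
| 40% | 4.5% | 7.7% | 12.3% |
| 30% | 7.7% | 18.7% | 37.0% |

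If RFA did better than cryotherapy, pC would exceed 50%, the numerator would be negative and the error would fall below 2.5%. The pooled test would then be conservative for a cryotherapy statement.

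**Step 3: how far the stated power depends on the 50%.** The documents do not show that 50% applies to the mix. Section 1.3 reports 55% at 12 months for cryotherapy in a mixed primary and rescue cohort, and 80% eventual response in refractory patients after a median of 24 months. Neither matches an endpoint limited to two treatments. With EndoRotor held at 80%:

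| Pooled control rate | Non-inferiority power | Superiority power |
|---|---|---|
| 40% | >99.9% | 99.5% |
| 50% | 99.6% | 92.1% |
| 55% | 98.2% | 80.8% |
| 60% | 94.0% | 63.2% |
| 70% | 68.4% | 22.5% |

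**Step 4: precision by intended system.** If half the subjects were intended for cryotherapy, each arm would have about 28 of them. At 80% vs 50% the 95% half-width is 1.96 × √((0.16 + 0.25)/28) = 0.24, or about 24 points.

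**The case against.** The strongest reply is that cryoablation is loose wording in two sample-size paragraphs. The title, the introduction, the randomization, the model and the formal hypotheses all use continued ablative therapy or control, and Section 7.8 applies the 50% to the active control. An investigator's-choice comparator is openly described and deliberate. This stands. A reader might infer that the trial cannot support its primary non-inferiority test. The documents do not bear that out, because the pooled test is a valid randomized comparison with continued ablative therapy.

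The plan also has some evidence for pooling. In the single-centre cohort in Section 1.3, 46 refractory patients had similar response rates whichever therapy followed. This counts, but the cohort is small and non-randomized, included mucosal resection and ran for a median of 24 months. A non-significant difference there does not show that the systems are equal within two treatments. Nor do the documents show that repeat RFA is worse: Section 1.1 says that neither ablative technique removes the submucosal fibroblasts. The direction of any shift is therefore unknown.

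Two further inferences go too far. One is that the system is chosen after allocation. Section 5.5.3 says only "The investigator will choose the system in this arm" and gives no timing; what is missing is a rule to declare it beforehand. The other is that no randomized comparison with either system can ever be recovered. Because randomization is within site, a site that uses a single system would preserve one. The plan neither requires nor relies on such sites.

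**Conclusion.** The point holds as a mismatch of comparator. Sections 4.7 and 7.3 attach the 50% rate and over 95% non-inferiority power to cryoablation, while 7.4 and 7.6 test a pooled arm whose composition the investigators decide. The pooled result supports a statement about continued ablative therapy. It supports one about cryoablation only if RFA does at least as well as cryotherapy or is not used.

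The size is conditional. With cryotherapy at 50%, RFA at an assumed 30%, an assumed half-and-half mix and EndoRotor at 40%, false non-inferiority to cryotherapy occurs about 19% of the time. If the systems respond alike there is no inflation. The RFA response and share are illustrations, not estimates, and the table covers only RFA rates at or below the cryotherapy rate.

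The planned power also rests on a control rate that has not been supported for the mix: superiority power falls from about 92% at 50% to 63% at 60%. The primary analysis need not be replaced. Which ablative system subjects should receive is a clinical matter on which this point takes no view.

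**What to change.** - **Sections 4.7 and 7.3:** replace cryoablation by continued ablative therapy (RFA and/or cryotherapy) for non-inferiority as well as superiority. Either support the 50% rate for that mix under the two-treatment endpoint, or show power over a range of pooled control rates as in the second table above.
- **Sections 5.2 and 5.5.3:** for every subject, before the envelope is opened, record on the baseline CRF the system intended if allocated to control: RFA, cryotherapy or both. The third category is needed because 5.5.3 allows the two to be combined.
- **Section 7.4:** keep the pooled comparison as primary and add intended system as a covariate. Report the EndoRotor-control difference with its 95% CI by intended system, labelled descriptive. Make any statement about cryotherapy only from the intended-cryotherapy group.

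The cost is one CRF field and some rewording, with no change in treatment. Intervals by intended system will be wide and the claim becomes narrower. The field has to be collected prospectively, because the intended system cannot be reliably reconstructed once the allocation is known.

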5.6 Follow-Up Procedures and Therapy Transitions

Surveillance endoscopy is performed in 3 months where there is visual inspection of the treated areas. Biopsies are taken from the areas treated with the respective device are sent to pathology to evaluate for the presence of intestinal metaplasia (Barrett's). If the samples are read as negative by Pathology (no Barrett's seen), the patient then undergoes another endoscopy in 3 months. If the results again are negative, the patient is declared to have a complete response to the treatment (EndoRotor® or ablative therapy).

If there is intestinal metaplasia (Barrett's) confirmed by the biopsy, the patient undergoes a second treatment with either the EndoRotor® or ablative therapy as described in Section 5.7. Two consecutive negative results at 3 month intervals between biopsies is required to consider these subjects complete responders.

If there is intestinal metaplasia (Barrett's) seen either at 90 days or at 180 days after either (EndoRotor® or cryotherapy / ablative therapy) second treatment, the patient is considered to have failed and will exit the study.

To evaluate the secondary endpoint of this study, "Percent reduction of the area with Barrett's esophagus that was resected or ablated during the initial treatment session through the final follow-up visits", percent reduction of the area with Barrett's esophagus will be determined by a decrease in overall length. Using the Prague criteria, both the circumference and maximal length of the Barrett's segment will be estimated. A percentage reduction in the length will be calculated by length measured at the follow up endoscopy divided by the total prior length.

Adverse events, as defined in Section 10.4, will be recorded from the index procedure (Day 0) through study completion and/or exit/withdrawal.

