3.5 Contraindications

Subjects with endoscopic and histologic evidence of esophageal endoadenocarcinoma at the time of therapy should not be treated with the EndoRotor.

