4.2 Overview of Study Design

This is a prospective, multi-center, randomized study to compare the safety and performance of the EndoRotor® Mucosal Resection System with continued ablative therapy in subjects with refractory dysplastic Barrett's Esophagus. Subjects must have failed 3 RFA treatments (failure of Barrett's to respond to RFA with a decrease of at least 50% of its length) and following 3 RFA failures have no endoscopic and histologic evidence of esophageal adenocarcinoma at the time of therapy. The subjects are randomized and treated (up to 2 times) with either the EndoRotor® which resects the affected mucosa and submucosa (down to the muscularis propria layer), or with cryotherapy or ablative therapy of the persistent lesions. Subjects will be followed with biopsies of the resected areas at the time of surveillance endoscopies every 3 months until they have 2 consecutive negative endoscopies and biopsies (6 months). Those who are positive after 2 treatments will exit the study and will be deemed treatment failures.

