4.3 Primary Endpoints

4.3.1 Primary Effectiveness Endpoint

Complete removal of areas of Barrett's metaplasia after no more than two treatments.

The primary effectiveness endpoint will be measured by post-treatment visual appearance on surveillance endoscopies and the findings on histology from biopsies taken of the treatment site at each endoscopy.

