7.2 Analysis Populations

The safety analysis population is defined as all subjects who are treated with either EndoRotor® or continued ablative therapy. Subjects will be analyzed as treated.

The primary effectiveness analysis population is intent to treat (ITT), defined as all subjects who are randomized. Subjects will be analyzed as randomized. Missing primary and secondary endpoint data will be imputed.

A supportive effectiveness analysis population is Per Protocol (PP). This population is a subset of ITT and requires that subjects be treated with either EndoRotor® or continued ablative therapy, meet all inclusion/exclusion criteria, and are evaluated for effectiveness at no fewer than two post-treatment visits 3 months apart. Subjects will be analyzed as treated. Missing data will not be imputed.

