7.5 Missing Data

1. If there are missing primary endpoint data, then ten imputations of missing binary primary endpoint will be produced using SAS PROC MI using the Markov chain Monte Carlo algorithm. The seed used to begin random number generation will be 20170623. The following variables will be used as predictors: site, subject's age, dysplasia (low-grade or high-grade), length of Barrett's lesion in cm, and duration of disease (months). Analysis with SAS PROC MIANALYZE will follow.
2. For the secondary endpoint, percentage reduction, ten imputations will be produced for the randomized cohort using SAS PROC MI. The seed used to begin random number generation will be 20170623. The Markov chain Monte Carlo method will be used to compute full imputations using the following variables: site, subject's age, dysplasia (low-grade or high-grade), length of Barrett's lesion in cm, and duration of disease (months). Analysis with SAS PROC MIANALYZE will follow.

The following secondary analyses will be performed to assess the sensitivity of the results to missing data for the primary effectiveness endpoint.

- The best-case scenario will assume success for all missing data treated with EndoRotor and failure for all missing data treated with control.
- The worst-case scenario will assume failure for all missing data treated with EndoRotor and success for all missing data treated with control.
- If the best and worst case analyses lead to different statistical conclusions, then a tipping point analysis will report the proportion of successes or failures for each arm at point the statistical conclusion would change.

A similar approach will be used for the continuous percentage secondary endpoint. Best case will assume 100% removal for EndoRotor® and 0% for control; worst case will assume 0% removal for EndoRotor® and 100% for control; If the results differ using the two imputation rules, then the imputed values will be incremented on 1% values until the point where the conclusion changes is identified.

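### A subject who is biopsy-positive after one treatment and is not re-treated has no defined outcome, and the natural reading of the plan is to impute one without using the positive biopsy

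*Combined protocol and SAP*

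**What the plan says.** The primary endpoint (4.3.1) is "Complete removal of areas of Barrett's metaplasia after no more than two treatments".

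Success (5.6): "Two consecutive negative results at 3 month intervals between biopsies is required to consider these subjects complete responders".

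Failure is always tied to a second treatment. Section 4.2 says "Those who are positive after 2 treatments will exit the study and will be deemed treatment failures". Section 5.6 fails a subject with metaplasia at 90 or 180 days after the "second treatment, the patient is considered to have failed and will exit the study". Scenarios 2 and 4 in 5.7.1 follow the same rule. A positive biopsy after the first treatment leads to re-treatment, not to an outcome.

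Section 4.14 covers withdrawal and loss to follow-up but gives no endpoint value for either.

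For the ITT population, 7.2 says "Missing primary and secondary endpoint data will be imputed". Section 7.5 specifies ten imputations by MCMC: "The following variables will be used as predictors: site, subject's age, dysplasia (low-grade or high-grade), length of Barrett's lesion in cm", plus duration of disease. No surveillance biopsy result, number of treatments or treatment arm is listed. Best-case, worst-case and, if those two disagree, tipping-point analyses are planned as sensitivity analyses.

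**The concern.** Take a subject who is positive at 3 or 6 months and then refuses, withdraws, is lost, or cannot be re-treated because of a complication. The protocol holds a biopsy showing residual Barrett's, and no later result contradicts it. On any ordinary reading of the endpoint this subject did not achieve complete removal. Yet the subject meets neither the success rule nor the failure rule, so an analyst following 7.5 would treat the endpoint as missing and draw it from a model that never sees the positive biopsy.

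At stake is the value of the primary endpoint for identifiable subjects, and therefore both reported response rates and possibly the difference between them. If the gap stays open, the choice is made after data exist, in a trial where the investigator who decides on re-treatment knows the arm.

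**Working it through.** **Inputs from the documents:** response rates 80% and 50%, 55 evaluable per arm, superiority power 91.6%, margin 10 points (7.3); two-sided 0.05 (7.1); 120 enrolled with 10 allowed as lost (4.5), so 60 per arm. I take 7.2 (ITT primary) as governing, although the Protocol Summary names a per-protocol primary analysis.

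**Assumed, not in the documents:** first-treatment clearance of 60% (EndoRotor) and 30% (control), and all stopping rates.

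**1. The plan's own figure.** Pooled two-proportion formula, n = 55:

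- null SE = √(2 × 0.65 × 0.35 / 55) = 0.0910
- alternative SE = √((0.16 + 0.25) / 55) = 0.0863
- power = Φ((0.30 − 1.96 × 0.0910) / 0.0863) = 92.1%

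This agrees with the stated 91.6%. Non-inferiority power is Φ(0.40 / 0.0863 − 1.96) = 99.6%, consistent with the stated figure of over 95%. The sample-size statement is not in question.

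**2. Effect per subject.** With non-responder scoring a stopper contributes 0 successes. If imputed, the stopper contributes q. At the planned rates q runs from 0.50 to 0.80, and is 0.65 if the arms are pooled, since arm is not a predictor. The shift in an arm of 60 is k × q / 60:

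| Stoppers k | q = 0.50 | q = 0.65 | q = 0.80 |
|---|---|---|---|
| 1 | 0.8 | 1.1 | 1.3 |
| 5 | 4.2 | 5.4 | 6.7 |
| 10 | 8.3 | 10.8 | 13.3 |

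**3. Effect on the difference (expected values).** First-positives number 24 (EndoRotor) and 42 (control). Success after re-treatment is (0.8 − 0.6)/0.4 = 0.50 and (0.5 − 0.3)/0.7 = 0.286.

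*30% and 5% of first-positives stop* (7.2 and 2.1 subjects):

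- Non-responder scoring: (36 + 16.8 × 0.50)/60 = 74.0%; (18 + 39.9 × 0.286)/60 = 49.0%. Difference 25.0.
- Pooled completer rate: (44.4 + 29.4)/(52.8 + 57.9) = 66.7%. Imputed: (44.4 + 4.8)/60 = 82.0%; (29.4 + 1.4)/60 = 51.3%. Difference 30.7.
- With arm in the imputation model: 44.4/52.8 − 29.4/57.9 = 33.3.

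*20% stop in both arms* (4.8 and 8.4 subjects):

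- Non-responder scoring: 45.6/60 = 76.0%; 27.6/60 = 46.0%. Difference 30.0.
- Pooled completer rate: 73.2/106.8 = 68.5%. Imputed: 81.5% and 55.6%. Difference 25.9.

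The pooled values of 66.7% and 68.5% also exceed the 50% and 28.6% chance of success these subjects would have had if re-treated. The imputation is therefore too generous even for the question of what would have happened had they continued.

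**4. Error rates.** 20,000 simulated trials per setting, 60 per arm. Stoppers are true failures and the arm rates count them as such. Ten imputations are drawn from the pooled completer rate and combined by Rubin's rules; the risk difference is unadjusted. The superiority null is 50% vs 50%; the non-inferiority null is 50% vs 60%. Nominal error in the EndoRotor direction is 2.5%.

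| Stoppers (EndoRotor vs control) | False superiority | False non-inferiority |
|---|---|---|
| 5 vs 5 | 2.0% | 1.7% |
| 5 vs 0 | 6.5% | 6.8% |
| 8 vs 2 | 7.0% | 7.6% |
| 10 vs 0 | 15.2% | 17.0% |
| 0 vs 5 | 0.7% | 0.5% |

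With non-responder scoring the same settings give about 2.0% to 2.6%. Adding arm alone to the imputation model does not help: 10 vs 0 then gives 19.6% for both tests.

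**The case against.** **Missing is an inference.** Sections 7.2 and 7.5 do not define the term or name this subject. The short endpoint wording in 4.3.1 could be read to make every non-success a failure. That reading is possible, but no section applies it, and applied to everyone it would leave 7.5 with nothing to impute. So the documents contain a gap with a likely consequence, not an explicit rule that scores known failures as successes.

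**Direction.** A reader might infer that the plan favours EndoRotor. The documents do not support that. With 20% stopping in both arms, imputation lowers the difference from 30.0 to 25.9 points, because control has more first-positives to inflate. Only an excess of stops in the EndoRotor arm pushes the other way.

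**The cancer rule.** Section 3.5 says that subjects with evidence of cancer "at the time of therapy should not be treated with the EndoRotor", and a reader might infer a bar in one arm only, producing unequal stopping. Section 4.2, inclusion 5 and exclusion 3 apply the no-cancer condition to all subjects, and 5.5.2 withholds both devices at the index procedure from anyone ineligible. What follows for re-treatment is unclear in both arms; a one-sided bar is not established.

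**Scenarios.** The 30%/5% case uses 9.3 of the 10 planned losses; the 20%/20% case needs 13.2 and exceeds them; 10 vs 0 puts every planned loss in one arm and one category. These are stress cases. The calculations also treat the baseline covariates as uninformative.

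**Existing safeguards.** "The worst-case scenario will assume failure for all missing data treated with EndoRotor and success for all missing data treated with control" is harsher on EndoRotor than non-responder scoring, and a conflict between the bounds triggers a tipping-point analysis. These might expose the problem but do not correct the primary estimate, and neither bound scores known positives as failures in both arms. The Per Protocol set does not help: it needs two post-treatment evaluations, so it drops a subject who stops after a single positive visit.

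**Conclusion.** The concern holds as a gap in outcome assignment that reaches the primary analysis. Followed as written, 7.5 can turn documented residual Barrett's into a success roughly 50% to 80% of the time, at 0.8 to 1.3 points per subject in an arm of 60. Inflation of both response rates is the firm result. The effect on the comparison depends on where stops fall: error stays at or below nominal if they are balanced or mainly in control, and reaches about 6.5% to 17% in the assumed splits where they concentrate in the EndoRotor arm. The size rests on assumed stopping and clearance rates and on unadjusted calculations; the gap in the rules does not.

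**What to change.** In 5.6 and 7.5, state that in the ITT primary analysis, in both arms, a subject whose last available surveillance biopsy is positive, with no later negative examination, is a non-responder whatever the number of treatments or the reason for stopping.

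Limit multiple imputation and the best-case, worst-case and tipping-point analyses to subjects whose outcome is truly unknown: those with no post-treatment biopsy at all, and those whose last biopsy is negative but lacks the second confirming negative, including those re-treated after an earlier positive. Add interim biopsy results and treatment arm to the imputation model.

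Reconcile Scenario 4 (5.7.1.4, follow-up to 12 months) with 5.7.4 (all exit after the 9-month visit). A subject re-treated at 6 months and negative at 9 months should not have the outcome decided by truncation of follow-up. Sections 3.5, 4.2, 4.12, 4.13 and 5.5.2 must also be reconciled on re-treatment when cancer is found, for both arms.

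Cost: protocol and SAP wording, lower response rates in both arms, and some power. If completers respond at 80% and 50% and 5 of 60 per arm stop and count as failures, the rates are 0.80 × 55/60 = 73.3% and 0.50 × 55/60 = 45.8%. Superiority power is then 87.6%, against the stated 91.6% for 55 evaluable per arm.
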